A Comparison of the Effects of Desflurane and Total Intravenous Anesthesia (TIVA) on Antioxidant System in Morbidly Obese Patients Undergoing Bariatric Surgery: A Randomized Trial

***[name]**, Asst. [name] of Anesthesiology and Reanimation, Inonu University Faculty of Medicine, Malatya, Turkey

[name], Asst. [name] of Anesthesiology and Reanimation, Inonu University Faculty of Medicine, Malatya, Turkey

[name], [name] of Anesthesiology and Reanimation, Inonu University Faculty of Medicine, Malatya, Turkey

[name], [name] of Physiology, Inonu University Faculty of Medicine, Malatya, Turkey

[name], [name] of Medical Biochemistry, Inonu University Faculty of Medicine, Malatya, Turkey

Address all correspondence to:

[name], Asst. [name] of Anesthesiology and Reanimation, Inonu University Medical Faculty, Malatya, Turkey

Mail: [contact]

[contact]

[contact]

A short title: **Antioxidant System Related Anesthesia in Morbidly Obese Patients**

Conflict of Interest:

The authors declare that they have no conflict of interest.

Funding Information:

None

Study Protocol

This trial was approved by the Local Ethic Committee of Inonu University (Protocol no: 2018/30, Approval Date: 07.03.2018). We conducted a prospective, randomized controlled clinical trial with 70 adult morbidly obese patients undergoing laparoscopic bariatric surgery at a university hospital.

Study Participants:

Morbidly obese patients with American Society of Anesthesiology (ASA) scores of III-IV, who aged 18–65 years old, and had a BMI>40 will be included in our study. Patients will be interviewed before surgery to obtain informed consent. Patients with pregnant or uncontrolled diabetes mellitus, cardiovascular disease, pulmonary disease, cerebrovascular disease, or drug and alcohol addiction were excluded. Patients who refused informed consent will be also excluded.

Preoperative Procedures:

All of the patients one day before surgery; hemoglobin, hematocrit, prothrombin time, active partial thromboplastin time, aspartate aminotransferase, alanine aminotransferase will be evaluated. Electrocardiography, posterior-anterior chest X-ray and preoperative anesthetic evaluations will be performed. Age, gender, height, weight, BMI, ideal body weight (IBW), ASA physical status and type of the surgery will be recorded in preoperative evaluation. On the day of surgery, patients will be taken to the operating room without premedication. Standard monitoring procedures will be used, including heart rate (HR), noninvasive blood pressure (NIBP), electrocardiogram (ECG), peripheral oxygen saturation (SpO2), and body temperature monitoring by esophageal probe. After the standard monitoring, invasive arterial monitorization will be performed to right radial artery under local anesthesia. BIS (Bispectral Index,

VISTATM Monitoring System) monitoring will perform to all patients. Two cerebral BIS sensors will glue to areas under the hairline and covered with tape to prevent exposure to light.

General Anesthesia:

A standardized general anesthesia protocol either desflurane or TIVA will be administered in all patients by an experienced anesthesiologist. After preoxygenation (100% 4 L/min O₂ for 3 min), propofol (1–2 mg/kg), rocuronium (0.8 mg/kg) and fentanyl (0.1 µg/kg) will be administered during the induction of anesthesia via intravenous (IV) route at doses calculated according to ideal body weights. End-tidal carbon dioxide (EtCO₂) will be continuously monitored after intubation. Tidal volume and ventilation rate will be adjusted to maintain EtCO₂ partial pressure of arterial blood at 35–45 mmHg. Rocuronium will be intermittently injected according to need based on Train of Four (TOF; Dräger AG, Lübeck, Germany) values. TOF responses will be assessed by ulnar nerve stimulation and adductor muscle response. 0.1–0.2 µg/kg fentanyl will be titrated for analgesia, as needed, if HR and/or mean arterial pressure (MAP) increased by 20% above baseline during surgery. Anesthesia will be maintained in desflurane group at inhalation in a 0.5 O₂ oxygen-air mixture (target MAC: 1-1.5, BIS values: 40 – 60, at the same times). Also anesthesia will be maintained in TIVA group with propofol and remifentanil infusion at inhalation in a 0.5 O₂ oxygen-air mixture (BIS values: 40 – 60). Desflurane or TIVA will be discontinued with the beginning of the skin sutures and the fresh gas flow was changed to 4 L/min of oxygen for both groups. In patients who will not experience complications during the surgery, sugammadex (IV, 2–4 mg/kg, Bridion®, MSD, Greenville, USA) will be then administrated to reverse residual muscle relaxation at the end of surgery.

Randomization:

Randomization was performed with the MedCalc for Windows (medcalc.com.tr.), version 16 statistical software. Seventy patients will be randomly allocated to two study groups:

Desflurane group (Group D, $n = 35$) and TIVA group (Group T, $n = 35$). Patients in both groups will be received a fresh gas flow of 4 L/min for the first 10 minutes and were then maintained with a fresh gas flow of 2 L/min. All patients will be mechanically ventilated with a tidal volume of 8 mL/kg based on ideal body weight and a frequency of 12–14 breaths/min using a Dräger Primus ventilator (Dräger AG, Lübeck, Germany). Age-related minimum alveolar concentration values will be determined and expressed as a percentage of volume. All patients will be received the standard surgical procedures determined by the same team of surgeons with experience in gastroenterology surgery. Pneumoperitoneum pressure will be ranged between 10 – 12 mmHg. Also pneumoperitoneum level will be 30 – 45 degrees. Surgical management of sleeve gastrectomy won't be changed in any way.

Outcome Measures:

HR, SpO₂, EtCO₂, mean arterial pressure (MAP), and BIS values will be recorded perioperatively. Blood samples will be taken for oxidative stress analysis at 15 minutes before anesthesia (T₀), perioperative period (1 hour after anesthesia induction) (T₁), and postoperative period (1 hour after awakening from anesthesia) (T₂). The blood samples will be kept in the biochemistry tubes under appropriate conditions (after centrifugation at -80 °C). Also anesthesia and surgery times, perioperative and postoperative complications will be recorded.

Postoperative Management:

Patients will be transferred to the post-anesthesia care unit (PACU) after surgery. Patients will be transferred to the general surgery intensive care unit when they achieved a score of 9 or higher on the Modified Aldrete score (range 0 –12; scores of 9 and above indicate that the patient can be discharged from the PACU). In all patients, postoperative analgesia will be achieved IV analgesic medication using appropriate doses of tramadol (0.5-1 mg/kg, IV) and paracetamol (1 gr, IV) at the time of beginning skin sutures.

Statistical Analysis:

On the basis of Han's study and using the power calculation method (OpenEpi, Version 3), assuming an alpha of 0.05 and a beta of 0.80, we calculated that 20 patients per group should be included in this study. Data will be analyzed using the Statistical Package for the Social Sciences program (SPSS 22.0, IBM). As some pre and anesthetic characteristics of patients will be distributed abnormally nonparametric statistics will be used. Quantitative data will be presented as mean or standard deviation and categorical data will be shown as numbers or percentages. Continuous variables will be compared between the groups using Mann-Whitney U-test. Categorical variables will be summarized using frequencies and percentages (%) and compared between the groups using Chi-Squared Test. The results will be evaluated at a 95% confidence interval at a significance level of $p<0.05$.

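### The T0 oxidative-stress sample is collected but not used: an unadjusted Mann-Whitney U-test is valid, but T0-adjusted rank ANCOVA would gain precision at almost no cost

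*Combined protocol and SAP*

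**What the plan says.** Under Outcome Measures in the combined protocol and SAP, "Blood samples will be taken for oxidative stress analysis at 15 minutes before anesthesia" (T0). Two further samples follow, one hour after induction (T1) and one hour after awakening (T2). T0 precedes any study anaesthetic, so it is a true pre-treatment measurement.

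Under Statistical Analysis, the only method for continuous variables is: "Continuous variables will be compared between the groups using Mann-Whitney U-test". The reason given for rank methods is: "As some pre and anesthetic characteristics of patients will be distributed abnormally nonparametric statistics will be used". The section names no covariate, change score or repeated-measures method, and no other section does so. It adds: "The results will be evaluated at a 95% confidence interval", without naming an estimate for the markers to which an interval would belong.

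On size, the same section states: "assuming an alpha of 0.05 and a beta of 0.80, we calculated that 20 patients per group should be included in this study". The Randomization section allocates 35 patients to each group.

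**The concern.** In a randomised comparison, a baseline value of the outcome usually explains part of its variation at follow-up. Adjusting for it removes that part from the error and leaves the treatment contrast unbiased. This plan pays for the T0 sample and then makes no use of it in the between-group test. At stake is the chance of detecting a real difference at T1 or T2 with 70 patients. There is also a small clarity gap, because the text does not expressly say that the T1 and T2 comparisons are on raw values.

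**Working it through.** **Inputs from the documents.** 35 per group (Randomization); 20 per group calculated, alpha 0.05 and a figure of 0.80 that appears to mean power (Statistical Analysis); samples at T0, T1 and T2 (Outcome Measures).

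**Inputs assumed.** rho (0 to 0.7), the effect size, equal SDs at each time, and a two-sided 5% test.

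**The plan's own figure.** No difference, SD or endpoint is given, so 20 per group cannot be reproduced. It can only be back-solved, on the assumption of a comparison of means, from d = (z_alpha + z_power) × √(2/20):
- two-sided, 80% power: (1.960 + 0.842) × 0.316 = 0.886 SD
- one-sided, 80% power: (1.645 + 0.842) × 0.316 = 0.786 SD
- two-sided, 0.80 taken literally as beta, so 20% power: (1.960 − 0.842) × 0.316 = 0.354 SD

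If the calculation was on proportions, no SD follows at all.

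**Variance of the group contrast relative to raw values.** With T0 adjustment it is 1 − rho²; for change from T0 it is 2(1 − rho).
- rho 0.3: adjusted 0.91, change 1.40
- rho 0.5: adjusted 0.75, change 1.00
- rho 0.7: adjusted 0.51, change 0.60

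**Approximate power.** For Mann-Whitney on normal data, power ≈ Φ(d × √(n/2 × 3/π) − 1.96). With n = 35 and d = 0.5 this is Φ(2.044 − 1.96) = 0.53. Dividing 2.044 by √0.91, √0.75 and √0.51 gives 0.57, 0.66 and 0.82 for rank adjustment. These approximations run slightly high, so the conclusions rest on simulation.

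**Simulated power** (normal data, 35 per arm, 20,000 trials per row):

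| Effect | rho | Mann-Whitney, raw | Rank ANCOVA | Linear ANCOVA | Mann-Whitney, change |
|---|---|---|---|---|---|
| 0.5 SD | 0 | 0.513 | 0.510 | 0.528 | 0.290 |
| 0.5 SD | 0.3 | 0.525 | 0.556 | 0.576 | 0.402 |
| 0.5 SD | 0.5 | 0.521 | 0.626 | 0.656 | 0.515 |
| 0.5 SD | 0.7 | 0.522 | 0.780 | 0.821 | 0.740 |
| 0.89 SD | 0.3 | 0.947 | 0.959 | 0.967 | 0.856 |
| 0.89 SD | 0.5 | 0.949 | 0.981 | 0.988 | 0.948 |
| 0.89 SD | 0.7 | 0.945 | 0.998 | 0.999 | 0.996 |

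Repeat runs agree within simulation error; at 0.5 SD and rho 0.5 they give about 62% for rank ANCOVA. With no true difference, every method rejects in 4.6 to 5.2% of trials.

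At 0.5 SD, Mann-Whitney would need about 38 / 45 / 63 per arm to match rank ANCOVA with 35. At the other back-solved effects, Mann-Whitney against rank ANCOVA at rho 0.3 / 0.5 / 0.7 is about 89% against 91 / 95 / 99% (0.79 SD) and 29% against 31 / 36 / 48% (0.35 SD).

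**Non-normal data.** With heavy tails (t, 3 df, unit SD) at 0.5 SD, Mann-Whitney has about 79%, rank ANCOVA 82 / 88 / 95% and linear ANCOVA 66 / 74 / 87%. The rank version keeps its advantage. The linear version falls below the plan's own test at rho 0.3 and 0.5.

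**Raw or change, chosen after seeing both.** With no true difference, the two statistics have correlation √((1 − rho)/2), which is 0.71 at rho 0 and 0.39 at rho 0.7. For two 5% normal tests with those correlations, the chance that at least one is significant is 8.3% and 9.4%. Simulation gives 9.1 / 9.0 / 9.5% at rho 0.3 / 0.5 / 0.7. The range is therefore about 8 to 9.5% for one marker at one time point.

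**The case against.** The strongest reply is that this is a choice between two valid tests. The Mann-Whitney U-test keeps its 5% error rate, and the plan gives a reason for working with ranks. The only effect size that can be tied to the documents is about 0.89 SD, and that itself rests on assumptions. At that size, 35 per arm already gives about 95% power, so adjustment adds 1 to 5 points. At rho near 0 it adds nothing. All of this stands, and it is why the point is minor.

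Three stronger readings are tempting, and the documents support none of them.
- *The analysis is biased or invalid.* It is not: randomisation protects the unadjusted comparison.
- *The trial has only about 52% power.* That figure belongs to an assumed 0.5 SD. The plan states no effect size, so no power shortfall can be read from it.
- *The plan leaves raw against change from T0 open and so inflates false positives.* Change from T0 is nowhere mentioned, and the plain reading is a comparison of recorded values. Change is merely not excluded. The 8 to 9.5% arises only if an analyst picked between the two after seeing results, which nothing in the documents suggests.

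Nor does rank ANCOVA beat change scores everywhere. By rho 0.85, at 0.5 SD, its advantage is gone (about 95% for each).

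**Conclusion.** The point holds as a minor efficiency improvement. A pre-treatment measurement of the outcome is collected and left out of the only between-group test. What is lost is precision: the contrast variance could fall by a fraction rho², which is 9%, 25% or 51% at rho 0.3, 0.5 or 0.7. In power at 35 per arm, that is about 3 to 26 points at 0.5 SD, 1 to 5 points at 0.89 SD, and nothing at rho near 0. These figures rest on assumed rho and effect sizes and on normal data; the heavy-tailed check points the same way. The choice of a primary marker and time point, and multiplicity across T1 and T2, are separate matters. The change below neither settles nor worsens them, because the plan already tests both times.

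**What to change.** Add to Statistical Analysis:

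> For each oxidative-stress marker, the groups will be compared at T1 and at T2 by rank (Quade) analysis of covariance with T0 as covariate, in place of the unadjusted test as the main analysis. A missing T0 will be given the overall mean rank, ignoring group. The unadjusted Mann-Whitney U-test will be reported as a sensitivity analysis, and change from T0 will not be tested. T0 will be described by group and not tested. For markers with only positive values, the T0-adjusted group ratio from a log-scale ANCOVA with its 95% CI will be given as a supporting estimate.

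Other continuous variables stay on the planned Mann-Whitney U-test. The method fits the plan's nonparametric approach and runs in the SPSS package it names: rank T0 and the outcome over all patients, regress outcome ranks on T0 ranks ignoring group, then compare the residuals between groups by one-way ANOVA.

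The cost is a few sentences, with no new samples or patients. On normal data, rank ANCOVA gives up about 4 points to linear ANCOVA at 0.5 SD and rho 0.7 (78% against 82%). It yields no direct effect estimate, hence the supporting ratio, which also gives the planned 95% interval something to describe. The missing-T0 rule matters. If patients without T0 were dropped, leaving 32 per arm, power at 0.5 SD would be about 52 / 58 / 74%, which cancels the gain at rho 0.3. With the mean-rank fill and 10% of T0 missing at random, it is about 55 / 61 / 74%, with type I error near 5%.

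### Does using only the chi-squared test for categorical variables make the complication comparisons unreliable with 35 patients per arm?

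*Combined protocol and SAP*

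**What the plan says.** The Statistical Analysis section has one rule for categorical data: they are summarised by counts and percentages and "compared between the groups using Chi-Squared Test". It does not say whether the statistic is continuity-corrected, gives no rule for small counts, and names no exact test. Significance is judged at 0.05, with sidedness not stated. The software is SPSS 22.0.

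The Randomization section allocates 70 patients equally, 35 to each arm. Under Outcome Measures, "perioperative and postoperative complications will be recorded". No complication types or expected rates are given. Because complications are categorical, the general rule covers them. It also covers baseline items such as gender, ASA class and type of surgery.

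**The concern.** The chi-squared p-value is a large-sample approximation, and the usual textbook caution applies when expected cell counts fall below 5. With 35 patients per arm, most uncommon complications will be in that range. Read literally, the plan would call 4 events against none a significant difference between the anaesthetics, although an exact test would not.

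Complications are the adverse events compared between the arms, so a difference wrongly declared there could be repeated as a safety finding. The remedy also looks cheap: one sentence sending sparse tables to an exact test.

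**Working it through.** **Inputs.** 35 per arm (Randomization); level 0.05 (Statistical Analysis). Assumptions: two-sided testing, and true complication rates between 1% and 30%, since the documents give none. The plan states no figure on this point that could be reproduced.

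**Step 1: how often counts are sparse.** With m events in total, the expected count per arm is m × 35/70 = m/2. It is below 5 when m < 10, a pooled rate below 10/70 = 14.3%. If both arms share a true rate r, m is Binomial(70, r):

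| r | P(m < 10) |
|---|---|
| 5% | 99.8% |
| 8% | 94.9% |
| 10% | 84.1% |
| 12% | 67.1% |
| 15% | 38.3% |
| 20% | 8.5% |

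Sparse tables are the norm up to about 8% and the minority from about 15%.

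**Step 2: which tables change verdict.** For 4 versus 0:
- Pearson: χ² = N(ad − bc)²/(product of margins) = 70 × (4 × 35 − 31 × 0)²/(35 × 35 × 4 × 66) = 4.24, p = 0.039.
- Yates correction: replace 140 by 140 − 35 = 105, giving χ² = 2.39, p = 0.122.
- Fisher: 2 × C(35,4)/C(70,4) = 2 × 52,360/916,895 = 0.114.

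Enumerating all 35-versus-35 tables with fewer than 10 events, these are the only splits where uncorrected Pearson and Fisher fall on opposite sides of 0.05:

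| Split | Pearson | Yates | Fisher | Boschloo |
|---|---|---|---|---|
| 4 vs 0 | 0.039 | 0.122 | 0.114 | 0.072 |
| 5 vs 0 | 0.020 | 0.063 | 0.054 | 0.034 |
| 6 vs 1 | 0.046 | 0.111 | 0.106 | 0.072 |
| 7 vs 1 | 0.024 | 0.060 | 0.055 | 0.038 |

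In no 35-versus-35 table is Fisher significant and Pearson not. Disagreement is not confined to expected counts below 5: 8 versus 2 (expected count 5) gives 0.040 and 0.084.

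**Step 3: is the planned test miscalibrated?** With the same true rate r in both arms, the false-positive rate is the sum, over all tables (a, b) with p < 0.05, of Bin(a; 35, r) × Bin(b; 35, r).

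| r | Uncorrected Pearson | Fisher |
|---|---|---|
| 1% | 0.06% | 0.0% |
| 5% | 3.6% | 0.3% |
| 8% | 5.5% | 0.9% |
| 10% | 5.7% | 1.3% |
| 15% | 5.3% | 2.2% |
| 20% | 4.9% | 2.5% |

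Among tables with fewer than 10 events only, Pearson gives 3.6%, 5.4%, 5.7% and 5.3% at rates of 5%, 8%, 10% and 15%. The planned test is therefore close to nominal or below it where its validity is questioned, and Fisher is well below nominal.

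**Step 4: what the switch would cost.** Since every disagreement is Pearson significant and Fisher not, the probability of disagreement equals the power lost by moving to Fisher. Using Fisher throughout, this is 20.8 percentage points for true rates of 2% versus 10%, and 17.2 points for 5% versus 15%. With equal rates, the two tests disagree in 3.4% of trials at 5% and 4.4% at 10%.

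**The case for a change.** The best argument for a change is that 4 versus 0 and 6 versus 1 fail Boschloo's test as well as Fisher's. Boschloo's is the less conservative of the two, so Fisher's conservatism does not explain everything. In addition, the plan's wording permits p = 0.039 or p = 0.122 for the same 4 versus 0 table, depending on the continuity correction. Such a choice is better fixed before the data are seen, and it recurs for each complication type.

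The ambiguity is real, and naming one test would have been tidier. The rest carries less weight. Boschloo's p-value takes the worst case over the unknown common rate, so exceeding 0.05 there does not show that Pearson errs at the rates that matter; Step 3 shows an excess of at most about 0.7 percentage points. At 5 versus 0 and 7 versus 1, Boschloo agrees with Pearson against Fisher, so a general call for an exact test would still leave the verdict dependent on which one is chosen. If the analyst applies the Yates correction, all four sparse disagreements with Fisher disappear. SPSS also prints Fisher's test for 2×2 tables, so an analyst meeting a sparse table has that result to hand.

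**Conclusion.** The observation is accurate, but no change to the plan is needed. The section omits a routine detail that analysts usually settle sensibly, and a mandatory exact test would be a trade-off rather than a repair. At the assumed rates the uncorrected chi-squared test exceeds its nominal level by at most about 0.7 points (5.7% against 5%). Fisher's test would hold the error at 0.3% to 1.3% for event rates of 5% to 10%, at a price of about 17 to 21 points of power in the two examples. For complications, that makes real harm harder to detect.

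The consequence is also limited. The title and the blood-sampling schedule direct the trial at oxidative stress; those measurements are continuous and are compared by the Mann-Whitney U-test. Neither that result nor the sample size depends on this choice.

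The conclusion rests on assumed complication rates, two-sided testing at 0.05, all 35 patients per arm being analysed, and the uncorrected statistic. Under the corrected one, the sparse-table disagreement with Fisher does not arise.

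### No primary oxidative-stress marker, time or contrast is named and testing is unadjusted, so a claimed difference could rest on either T1 or T2

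*Combined protocol and SAP*

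**What the plan says.** Under Outcome Measures, the oxidative-stress outcome is described only by its sampling scheme: "Blood samples will be taken for oxidative stress analysis at 15 minutes before anesthesia" (T0), then one hour after induction (T1) and one hour after awakening (T2). No marker is named or counted. No marker or time is ranked above another.

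Under Statistical Analysis, one rule covers all such data: "Continuous variables will be compared between the groups using Mann-Whitney U-test". The threshold follows: "The results will be evaluated at a 95% confidence interval at a significance level of" 0.05. The section gives no testing order, no adjustment and no repeated-measures model. It does not say whether the groups are compared on the value at a time or on the change from T0.

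The sample-size sentence does not fill the gap. It cites an earlier study, sets its error rates by "assuming an alpha of 0.05 and a beta of 0.80", and ends "we calculated that 20 patients per group should be included in this study". It gives no endpoint, effect size or standard deviation. The Randomization section then allocates 70 patients, 35 per group.

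**The concern.** The title question is whether the two anaesthetics differ in their effect on the antioxidant system. A Mann-Whitney test compares two groups on one measurement at a time, so the stated rule gives at least two post-treatment tests per marker, one at T1 and one at T2. Nothing in the plan prevents either from carrying the overall conclusion.

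Two things are at stake. If a claim may rest on whichever of two or more tests falls below 0.05, its false-positive risk exceeds 5%. Whatever the size of that excess, a reader also cannot tell which result was meant to be decisive, for example when T1 and T2 disagree.

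**Working it through.** **1. The plan's own figure.** The 20 per group cannot be reproduced, because no effect size is given. Solved backwards with "assuming an alpha of 0.05 and a beta of 0.80" read as 80% power, it implies a standardised difference of (1.960 + 0.842) × √(2/20) = 0.89 two-sided, or (1.645 + 0.842) × √(2/20) = 0.79 one-sided. Neither value identifies a marker, time or contrast.

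**2. Inputs for the error rate.** From the documents: a per-test level of 0.05, two post-baseline times and 35 per group. Assumed: one marker, one fixed contrast, two-sided tests, no true difference, and a conclusion that either test may carry. The correlation between the T1 and T2 measurements is not given, so a range is shown. T0 is left out because it precedes treatment.

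**3. Formulas.** If the tests are independent, the risk is 1 − 0.95² = 0.0975. If they are correlated, it is 1 − P(|Z₁| ≤ 1.96 and |Z₂| ≤ 1.96), with Z₁ and Z₂ bivariate normal. As a check, pairs of Mann-Whitney tests were simulated on normal data with no difference, 35 per group, 20,000 runs per setting.

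| Correlation | Normal calculation | Mann-Whitney simulation |
|---|---|---|
| 0 | 9.75% | 9.6% |
| 0.5 | 9.1% | 9.0% |
| 0.8 | 7.8% | 8.0% |
| 0.9 | 7.0% | 7.0% |
| 0.95 | 6.5% | 6.3% |

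A single test in the same simulations rejected in 4.8% to 5.0% of runs. The excess therefore comes from having two chances, not from the test itself.

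**4. What the table leaves out.** It fixes one marker and one contrast. Trying several markers, or both value and change from T0, raises the risk. The number of markers is not stated, so no figure is given for that case.

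**5. Power at a Holm step.** If 20 per group gives 80% power two-sided, the noncentrality at 35 per group is 2.802 × √(35/20) = 3.706. Holm's first step over two tests uses 0.05/2, with critical value 2.241. By normal approximation:
- effect as assumed: Φ(3.706 − 2.241) = 93%;
- true effect 80% of that assumed: Φ(0.8 × 3.706 − 2.241) = 77%;
- original calculation one-sided: Φ(2.486 × √(35/20) − 2.241) = 85%.

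With more tests the critical value rises and these figures fall.

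**The case against.** The strongest objection is that the plan never adopts an either-test rule. It sets a threshold for each test and no rule for the overall conclusion. Reporting T1 (during surgery) and T2 (after awakening) as answers to two separate questions would be equally compatible with the text, and whether such questions in a small biomarker trial need joint error control is partly a matter of judgement. This stands as a limit on the numbers: 7-10% describes a practice that the plan permits, not one it prescribes. It does not remove the gap. The plan does not call itself exploratory, and a single sample-size calculation at alpha 0.05 suggests one decisive comparison, which is nowhere identified.

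The correlation is also assumed. Above 0.9 the risk drops below 7%, tending to 5% as the correlation approaches 1. So 7% is not a floor. Nor is 10% a ceiling, since the contrast and the number of markers are open.

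Finally, the earlier study behind the sample size may have used an endpoint that was also intended as primary here. That is possible, and a reader should not infer that no endpoint was ever chosen. The documents support only the statement that none is given in them.

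**Conclusion.** The concern holds in a limited form. The plan states no primary marker, time or contrast and tests at an unadjusted 0.05, so a claim of difference could rest on either T1 or T2. For one marker, one fixed contrast and an either-test conclusion, the false-positive risk is about 7-10% for assumed correlations of 0.9 down to 0, and about 6.5% at 0.95.

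Three stronger readings are tempting and not supported:
- That the trial's error rate simply is 7-10%. The figure depends on an unstated decision rule and an unstated correlation.
- That the rate reaches some much larger value because many markers will be tested. The documents give no marker count.
- That 35 per group makes a multiplicity correction cheap in power. That rests on an effect size the documents do not give, and on reading the stated beta as power.

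This should be corrected because it bears on the trial's main conclusion, although the inflation that can be shown from the documents is modest.

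**What to change.** Before between-group results are seen, name one oxidative-stress marker, at one post-baseline time, with one stated contrast (value or change from T0), as the primary outcome. Test it by the planned Mann-Whitney test at two-sided 0.05 and rest the trial's conclusion on it.

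For the other markers and times, choose one of two routes and write it down:
- test them by Holm, only if the primary is significant; or
- report Hodges-Lehmann differences with 95% confidence intervals and make no significance claims.

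The protocol mixes past and future tense, so it is unclear how far the trial had progressed when it was written. If results have already been seen and no earlier dated record identifies the primary, label all marker comparisons exploratory. Applying Holm at that stage would not restore 5%, because a contrast picked after seeing the data is itself a selection that Holm does not account for.

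The cost is SAP wording, plus an interval for each secondary comparison if the estimation route is taken. The primary keeps the full 0.05. Some secondary differences with p just under 0.05 can no longer be claimed, and the power left at any Holm step depends on an effect size the documents do not give.
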